Official Title:	Pilot Study of Weekly Brentuximab Vedotin or Brentuximab Vedotin Plus Nivolumab Every 3 Weeks in Patients with CD30+ Malignancies Refractory to Every \geq 3 Week Brentuximab Vedotin
NCT Number:	NCT01703949
Document Type:	Study Protocol and Statistical Analysis Plan
Date of Document:	January 31 st , 2023

UNIVERSITY OF WASHINGTON SCHOOL OF MEDICINE
FRED HUTCHINSON CANCER CENTER

**A Pilot Study of Weekly Brentuximab Vedotin or Brentuximab Vedotin Plus
Nivolumab Every 3 Weeks in Patients with CD30+ Malignancies Refractory to
Every \geq 3 Week Brentuximab Vedotin**

**Protocol Version Date: 12/15/2022
Previous Version: 11/02/21**

Principal Investigator

[name], FACP
Professor, UW
Member, FHCC
Fred Hutchinson Cancer Center
[name]
[name]
[contact]

Co-Investigator

[name]
Assistant Professor of Medicine, UW
Assistant Professor, FHCC
Fred Hutchinson Cancer Center
[name]
[name]
[contact]

This trial is supported by Seattle Genetics, Inc.

SCHEMA

ARM A (Closed to Accrual)
Registration

Brentuximab vedotin 1.2 mg/kg IV

Given Weekly 3 of 4 Weeks in a 28 day Cycle for Up to 4 Cycles

ARM A DOSING SCHEMA (Closed to Accrual)

EACH CYCLE (UP TO 4 CYCLES TOTAL)				
Chemotherapy	Treatment Day (Actual treatment dates may vary up to +/- 2 days)			
	1	8	15	22
Brentuximab vedotin 1.2 mg/kg (maximum 120 mg) IV over approximately 30 minutes	X	X	X	(Rest)

Follow-up will be performed 3 - 5 weeks following final cycle; then per standard of care.

ARM B (Open to Accrual)

Registration

Brentuximab vedotin 1.8 mg/kg IV

Given every 3 weeks (21 day cycle) for Up to 4 Cycles

ARM B DOSING SCHEMA (21-day cycle) (Open to Accrual)

EACH CYCLE (UP TO 4 CYCLES TOTAL)				
Chemotherapy	Treatment Day (Actual treatment dates may vary up to +/- 2 days)			
	Cycle 1	Cycle 2	Cycle 3	Cycle 4
	Day 1	Day 1	Day 1	Day 1
Brentuximab vedotin 1.8mg/kg IV	X	X	X	X
Nivolumab 3mg/kg IV	X	X	X	X

Follow-up will be performed 3 - 5 weeks following final cycle; then per standard of care.

TABLE OF CONTENTS

1.0 OBJECTIVES	5
2.0 BACKGROUND	5
3.0 DRUG INFORMATION	8
4.0 STAGING CRITERIA	9
5.0 ELIGIBILITY CRITERIA.....	9
6.0 REGISTRATION.....	10
7.0 TREATMENT PLAN	10
8.0 DOSE LIMITING TOXICITIES AND DOSAGE MODIFICATIONS.....	12
9.0 CONCOMITANT THERAPY	14
10.0 CORRELATIVE STUDIES	14
11.0 STUDY CALENDAR.....	14
12.0 CRITERIA FOR EVALUATION AND ENDPOINT DEFINITIONS	17
13.0 STATISTICAL CONSIDERATIONS.....	17

1.0 OBJECTIVES

1.1 Primary objectives

1.1.1. ARM A:

To estimate the response rate following weekly brentuximab vedotin (1.2mg/kg 3 of 4 weeks for up to four 28-day cycles) in patients with lack of response (<PR) or progression following brentuximab vedotin and demonstrating persistent expression of CD30.

1.1.2 ARM B:

To evaluate the response rate of combination brentuximab vedotin and nivolumab in patients with lack of response (<PR) or progression within 6 months following brentuximab vedotin

1.2 Exploratory objectives (will be completed as feasible, based on availability of data collected in the course of standard clinical assessments/follow-up)

1.2.1. To monitor clinical outcome following the study treatment regimen.

1.2.2. To estimate the frequency of CD30 loss in patients following resistance to brentuximab vedotin.

1.2.3. To describe the pattern of CD30 expression (membranous, cytoplasmic, golgi) in comparison to the pre-brentuximab vedotin expression.

1.2.4. To semi-quantitatively estimate and compare the surface density of CD30 pre and post brentuximab vedotin as measured by flow cytometry.

1.2.5. To correlate response with CD30 density as measured by flow cytometry

1.2.6. To evaluate the tolerability of the weekly regimen in patients previously exposed to brentuximab vedotin. To explore the tolerability of brentuximab vedotin and nivolumab in patients previously exposed to brentuximab vedotin in a 21-day cycle.

2.0 BACKGROUND

2.1 Rationale for development of new lymphoma therapies

Lymphoma is the seventh most common cancer in the United States. There are approximately 75,000 new diagnoses of lymphoma each year in the United States and approximately 30% of these patients may be cured with anthracycline-based chemotherapy regimens. Unfortunately, most of these patients will fail their initial therapy and will require a more aggressive treatment in an attempt to induce a remission [1-7]. For patients with aggressive lymphoid malignancies such as diffuse large B-cell lymphoma and Hodgkin's lymphoma, high dose therapies (HDT) followed by autologous stem cell transplantation (ASCT) have been shown to improve both progression-free and overall survival [8-10]. A number of factors have been shown to be predictive of improved outcome following HDT and ASCT. Among these factors, some of the most important predictors include sensitivity of the disease to cytoreductive chemotherapy, disease bulk at the time of transplant, and patients' overall performance status [11-16].

However, many patients are either not candidates for HDT and ASCT or will relapse following this procedure, indicating a need for novel therapies for this group of patients.

2.2 CD30 as a target for lymphoma therapy

CD30, a cell surface antigen and member of the TNF superfamily group of receptors, is expressed on several malignancies including Hodgkin's lymphoma (HL), anaplastic large cell lymphoma (ALCL), Kaposi's sarcoma (KS), cutaneous T cell lymphomas (CTCL), diffuse large B-cell lymphoma (DLBCL), some follicular lymphomas, and other lymphoproliferative diseases [17, 18]. Importantly, the expression of CD30 is thought to be very limited on normal tissues primarily limited to a subset to T-cells. These features make CD30 an attractive target for anti-lymphoma therapy in the subset of diseases where its expression is documented.

2.3 Every 3 week dosing of brentuximab vedotin in HL and ALCL

Based on the potential limited expression of CD30 on normal tissues, preclinical data, and the high-level expression on HL and ALCL, the antibody drug conjugate (ADC), brentuximab vedotin (BV) was evaluated in these patient populations [19]. BV is comprised of a chimeric mouse-human anti-CD30 monoclonal antibody with the addition of a dipeptide linker that enables the attachment of Monomethyl auristatin E (MMAE), a potent anti-microtubule agent. Specifically, BV is thought to bind CD30, followed by internalization and intracellular release of MMAE after lysosomal degradation. MMAE then binds to tubulin within the cell and induces cell cycle arrest and apoptosis [19]. In a large, multi-center phase II trial presented by Chen et al, the safety and efficacy of brentuximab vedotin were evaluated in patients with HL recurring after ASCT. A total of 102 patients were enrolled and given 1.8 mg/kg IV brentuximab vedotin every 21 days as outpatient 30-minute infusions for up to 16 cycles [20]. Patients had a median of 3.5 (1-13) prior systemic chemotherapy treatments (excluding ASCT). The objective response rate (ORR) was 75% (76 of 102 patients), with CR in 34% (35 of 102). For patients with CR, the median duration of response (DOR) had not been reached (0.3 + to 61.4+ weeks). A similar study was presented by Shustov et al evaluating BV in relapsed/refractory ALCL [21]. In this series of 58 ALCL patients who had received a median of 2 prior regimens, an ORR of 86% was observed with a CR rate of 57%.

The most common Grade 3-4 adverse events (AEs) occurring in patients from the above studies were neutropenia (21%); peripheral sensory neuropathy (8-10%); anemia (2-10%); and thrombocytopenia (9-10%) with 21% of patients discontinuing therapy due to an AE [20].

2.4 Weekly dosing of brentuximab vedotin

As part of the development of this agent, a weekly regimen given on Days 1, 8, and 15 of a 28-day cycle was evaluated [22]. The MTD of this regimen was found to be 1.2 mg/kg (capped at 120 mg). In this study of 44 patients (38 HL, 5 ALCL, 1 peripheral T cell lymphoma), tumor regressions were observed in 85% of patients with ORR and CR rates of 59% and 34%, respectively. Importantly, the toxicity profile of this regimen from this small study was comparable to the every 3 week regimen.

Nivolumab is a human IgG4 anti-PD-1 antibody which blocks this T cell inhibition, thereby enhancing anti-tumor T cell activity¹⁶. Nivolumab is now FDA approved for treatment of relapsed/refractory cHL patients based on two studies¹⁷. Nivolumab showed an objective response rate of 65% in the pooled analysis of 95 patients treated on the phase I CheckMate-039 trial and phase II CheckMate-205 trial¹⁷. The patients in these studies were heavily pre-treated with chemotherapy, autologous stem cell transplant and novel antibody drug conjugate, Brentuximab-Vedotin. Nivolumab was overall well tolerated, no grade 4-5 drug related toxicities, and mostly mild grade 1-2 rash, pruritis and diarrhea were reported. Five patients had reversible Grade 3 drug related toxicities.

2.7 Combination therapies of brentuximab and checkpoint inhibitors

Preclinical data indicate that through disruption of the microtubule network, brentuximab vedotin induces apoptotic cell death, and can initiate a localized antitumor immune response (i.e., immunogenic cell death) through the induction of endoplasmic reticulum (ER) stress.²⁵ Based on these data investigators have hypothesized that brentuximab vedotin could synergize with immune checkpoint inhibitors. To test this hypothesis a phase I/II trial was carried out and the data were recently presented showing that 3mg/kg of nivolumab and 1.8mg/kg brentuximab could be safely administered together every 21 days.²⁶ This study showed that these agents could be safely delivered together, though an increase in infusion reactions mandated use of premedications prior to BV. Importantly, these investigators observed an overall response rate

of 90% and complete response rate of 62% suggesting at least additivity in anti-tumor response noting that none of the patients on this trial were known to have disease that was refractory to either agent. Arm B of this trial will build on these data by evaluating patients with BV-refractory disease and will allow nivolumab refractory patients to be enrolled to truly test the potential synergy of these agents.

2.8 Summary

Data to date indicate that BV can induce remissions in the majority of patients in a 21 day, single dose cycle, but the majority will either not respond or relapse. This protocol is designed to evaluate BV in the setting of BV-refractory disease. The first cohort (Arm A) using BV was evaluated and showed only modest activity and was closed. The second cohort (Arm B) will test the combination of BV with nivolumab in a 21-day cycle. We thus hypothesize that through this iterative multi-arm study we will be able to identify a BV dosing scheme or combination that may show acceptable safety and efficacy in patients with prior BV exposure and importantly BV-resistant disease.

3.0 **DRUG INFORMATION**

3.1 General Information

Brentuximab vedotin (BV) is a CD30-directed antibody-drug conjugate (ADC) that has been approved by the U.S. Food and Drug Administration (FDA) for use in patients with HL after failure of ASCT or failure of at least two prior treatment regimens in patients who are not candidates for ASCT, and for use in patients with systemic ALCL after failure of at least one prior regimen. BV is marketed in the United States under the name ADCETRIS™ by Seattle Genetics, Inc.

BV used under this study will be provided by Seattle Genetics and will be identical to the commercially marketed product.

Nivolumab will be obtained from commercial sources and administered as standard of care.

3.2 Description

Brentuximab vedotin (BV) is a sterile, preservative-free, white to off-white lyophilized cake for reconstitution for IV administration. BV will be supplied by Seattle Genetics in single-use, Type 1 borosilicate glass vials with FluroTec®-coated butyl rubber stoppers and aluminum seals. Each vial of the product contains BV, trehalose, sodium citrate, and polysorbate 80. The drug product vial is reconstituted with the appropriate amount of Sterile Water for Injection.

Vials containing brentuximab vedotin must be stored under refrigeration at 2-8°C.

Chemical and physical stability of the reconstituted brentuximab vedotin drug product has been demonstrated for 24 hours at 2-8°C and 25°C. However, brentuximab vedotin does not contain preservatives; therefore, from a microbiological standpoint, opened and reconstituted vials should be used immediately. If not used immediately, the in-use storage should not be longer than 24 hours under refrigeration at 2-8°C. It is recommended that brentuximab vedotin vials and solutions be protected from direct sunlight until the time of use.

Nivolumab will be from commercial supplies and all relevant information is available from the package insert.

4.0 STAGING CRITERIA

- 4.1 The Ann Arbor staging criteria will be utilized. Staging should be the highest stage established from the time of diagnosis.

5.0 ELIGIBILITY CRITERIA

5.1 Inclusion Criteria

5.1.1. Relapsed or refractory CD30+ lymphoma that has either achieved <PR to brentuximab vedotin (minimum of 2 cycles), progressed while receiving brentuximab vedotin, or progressed within 6 months of the last dose of brentuximab vedotin.

5.1.2. Documented expression of CD30 on tumor cells

5.1.3. ANC >1,000/ μ L.

5.1.4. Platelets >50,000/ μ L.

5.1.5. Serum creatinine <1.5 mg/dL OR creatinine clearance >60 mL/min.

5.1.6. Bilirubin <1.5 x ULN.

5.1.7. AST and ALT <2.5 x ULN.

5.1.8. Measurable disease by CT or similar (e.g. MRI) criteria (>1.5 cm). (Patients with cutaneous lymphoma only require measurable disease by Olsen Criteria²⁷.)

5.1.9. Resolution of all non-hematologic brentuximab vedotin-related and nivolumab-related AEs to <Grade 2.

5.1.10. Age \geq 18 yrs at the time of the first dose of study drug.

5.1.11. All patients must be informed of the investigational nature of this study and have given written consent in accordance with institutional and federal guidelines.

5.1.12. Patients must be anticipated to complete at least 2 cycles of chemotherapy on study.

5.1.13. Expected survival if untreated of >90 days.

5.2 Exclusion Criteria

5.2.1. Prior transplant within 100 days.

- 5.2.2. Radioimmunotherapy within 12 weeks.
- 5.2.3. Known HIV or hepatitis B positivity or prior PML.
- 5.2.4. Active infection or other medical condition which would preclude treatment in the opinion of the principal investigator. This would include a corrected DLCO of <60% predicted or symptomatic interstitial lung disease.
- 5.2.5. ECOG performance status >2.
- 5.2.6. Known active CNS involvement.
- 5.2.7. Peripheral neuropathy >Grade 1 if due to brentuximab vedotin or any peripheral neuropathy >Grade 2.
- 5.2.8. Intolerance to brentuximab vedotin.
- 5.2.9. Concurrent use of other anti-cancer agents or experimental treatments.
- 5.2.10. No current or prior autoimmune disease with the exception of vitiligo and autoimmune alopecia (Arm B only).
- 5.2.11. Pregnancy or breastfeeding. (Females of childbearing potential must have a negative serum or urine beta human chorionic gonadotropin (β -hCG) pregnancy test result within 7 days prior to the first dose of brentuximab vedotin. Females with false positive results and documented verification that the patient is not pregnant are eligible for participation. Females of non-childbearing potential are those who are postmenopausal greater than 1 year or who have had a bilateral tubal ligation or hysterectomy. Females of childbearing potential and males who have partners of childbearing potential must agree to use 2 effective contraceptive methods during the study and for 6 months following the last dose of brentuximab vedotin or 6 months following the last dose of nivolumab, whichever is later.)

6.0 REGISTRATION

- 6.1 Patients will be registered by research staff prior to the start of protocol therapy.

7.0 TREATMENT PLAN

- 7.1 For treatment or dose modification related questions, please contact [name] at [contact]. Dose adjustment of nivolumab may follow the US package insert (opdivo.com)

- 7.2 Each cycle of therapy is given every 21 days. Up to 4 cycles of chemotherapy will be administered on protocol. Following protocol therapy, patients may go on to receive other therapy at the discretion of their physician. Brentuximab vedotin will no longer be supplied by the study.

ARM B (Open to Accrual)				
EACH CYCLE (UP TO 4 CYCLES TOTAL)				
Chemotherapy	Treatment Day (Actual treatment dates may vary up to +/- 2 days)			
	Cycle 1	Cycle 2	Cycle 3	Cycle 4
	Day 1	Day 1	Day 1	Day 1
Brentuximab vedotin 1.8mg/kg (maximum 180 mg) over approximately 30 minutes	X	X	X	X
Nivolumab 3 mg/kg	X	X	X	X

7.3 Dose and Administration

Arm B: BV will be administered on Day 1, of each 21 day cycle. The dose of BV is 1.8 mg/kg and is administered by outpatient IV infusion given over approximately 30 minutes. In the absence of infusion toxicities, the infusion rate for all patients should be calculated in order to achieve an infusion period of approximately 30 minutes. BV must not be administered as an IV push or bolus. BV should be administered through a dedicated IV line. BV cannot be mixed with other medications.

Dosing should be based on actual weight except for patients weighing greater than 100 kg; dose will be calculated based on 100 kg (i.e., maximum dose of 180 mg) for these individuals. BV dose should be rounded to the nearest whole number of milligrams.

BV should be given prior to nivo whenever possible if both are given on the same dosing day; a recommended ≥ 30 minute window should be planned between completion of BV and initiation of nivo infusion.

Dose modification in response to toxicity is described under section 8.0 below.

Nivolumab is administered over 30-60 min as standard of care for relapsed HL and will be obtained from commercial sources. Other drugs should not be co-administered through the same IV line (e.g., brentuximab vedotin).

7.4 Required Premedication and Postmedication

Routine premedication is required prior to the first dose of BV and nivolumab as described below. However, patients who still experience a Grade 1 or Grade 2

infusion-related reaction may receive subsequent BV infusions with additional premedication per institutional standard, as described below.

- 7.4.1 Nausea/vomiting prophylaxis: Nausea vomiting prophylaxis is not required by this protocol or for this agent; however it may be used per institutional practice.
- 7.4.2 Infusion reaction prophylaxis: Infusion reaction prophylaxis should include 100mg of hydrocortisone (or equivalent) and 25mg of diphenhydramine (or institutional equivalent) prior to dosing.
- 7.4.3 Infection prophylaxis: Infection prophylaxis is not required by this protocol or for this agent; however it may be used per institutional practice and could be considered for those with extensive pretreatment (e.g. transplantation, multiple prior therapies), cytopenia (lymphopenia, neutropenia), and/or recurrent infections. In these situations prophylaxis or monitoring for agents such as PCP, HSV, VZV, GNR, and/or CMV could be considered.

7.5 Management of Infusion Reactions

Infusion-related reactions may occur during the infusion of BV or nivolumab. All infusions are administered at a site properly equipped and staffed to manage potential infusion-related reactions, including anaphylaxis. Supportive measures will be given as appropriate throughout the treatment according to institutional standards.

A patient who experiences a Grade 1 or Grade 2 infusion-related reaction may receive subsequent BV infusions with additional premedication according to institutional standards.

Criteria for removal from protocol treatment:

- 7.5.1 Documented progression of disease.
- 7.5.2 Development of any related Grade 4 non-hematologic toxicity or other dose limiting toxicity as defined under section 8.0.
- 7.5.3 Development of any other unacceptable toxicities unless prophylactic measures can be taken for subsequent cycles.
- 7.5.4 Delay of a treatment cycle for more than 4 weeks due to adverse events.
- 7.5.5 Completion of protocol treatment (maximum of 4 cycles).
- 7.5.6 The patient may withdraw from the treatment at any time for any reason.

8.0 DOSE LIMITING TOXICITIES AND DOSAGE MODIFICATIONS

Parameters for retreatment and treatment modifications are as follows:

8.1 Modifications for Hematologic Toxicity

Subsequent cycles of therapy will not begin until the ANC is $\geq 1,000/\mu\text{L}$ and the platelet count is $\geq 50,000/\mu\text{L}$. Therapy will be delayed a maximum of 4 weeks until these values are achieved for Day 1 of each cycle. Mid-cycle doses will not require delay due to

hematologic toxicity. Hematopoietic growth factors and blood product support is allowed.

8.2 Modifications for Impaired Renal Function

Serum creatinine must be $<1.5\text{mg/dL}$ or an *estimated* or measured creatinine clearance $>60\text{ mL/min}$ on Day 1 of each cycle (labs may be drawn up to 3 days prior to Day 1). If these values are not met, treatment may be delayed for up to 4 weeks. If these values do not recover within 4 weeks, the patient will be removed from protocol treatment.

8.3 Modifications for Impaired Liver Function

Total bilirubin must be <1.5 times the upper limit of normal, and ALT and AST <2.5 times the upper limit of normal on Day 1 of each cycle (labs may be drawn up to 3 days prior to Day 1). If these values are not met, treatment may be delayed for up to 3 weeks. If these values do not recover within 4 weeks, the patient will be removed from protocol treatment.

8.4 Modifications for study treatment-related peripheral neuropathy

Note: these rules apply to **EVERY** dose of study drug and are relevant for treatment-emergent AEs only.

Table 1. Dose Modification Guidelines for Treatment-Related Peripheral Neuropathy

Toxicity	Grade 1	Grade 2	Grade 3 or Grade 4
Neuropathy: Motor	Continue at the same dose and schedule	Withhold dose until toxicity is Grade ≤ 1 or has returned to baseline. First occurrence: Reduce dose to 1.2mg/kg . Second occurrence: Omit Day 8 dosing from subsequent cycles. Third occurrence: patient will be removed from study.	Discontinue treatment at the discretion of the Sponsor-Investigator.
Neuropathy: Sensory	Continue at the same dose and schedule.	Withhold dose until toxicity is Grade ≤ 1 or has returned to baseline. First occurrence: Reduce dose to 1.2mg/kg . Second occurrence: Omit Day 8 dosing from subsequent cycles. Third occurrence: patient will be removed from study.	Discontinue treatment at the discretion of the Sponsor-Investigator.

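### In Arm B, the only open arm, the Table 1 action for a second Grade 2 neuropathy (omit Day 8) cannot be carried out, because brentuximab vedotin is given on Day 1 only (minor)

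*Combined protocol and SAP*

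**What the plan says.** The Schema shows Arm A (weekly BV, 1.2 mg/kg on Days 1, 8 and 15 of 28) as closed and Arm B as open. For Arm B, section 7.3 states: "BV will be administered on Day 1, of each 21 day cycle", at 1.8 mg/kg. The same section sends the reader to section 8 for dose changes: "Dose modification in response to toxicity is described under section 8.0 below". Section 7.2 caps treatment: "Up to 4 cycles of chemotherapy will be administered on protocol".

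Table 1 in section 8.4 applies to every dose of study drug and is not limited to one arm. In both the motor and the sensory row, the Grade 2 cell reads as follows:

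- At any occurrence: "Withhold dose until toxicity is Grade" 1 or less, or back at baseline.
- First occurrence: reduce to 1.2 mg/kg.
- Second occurrence: "Second occurrence: Omit Day 8 dosing from subsequent cycles".
- Third occurrence: "Third occurrence: patient will be removed from study".

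The last column covers Grade 3 and Grade 4 together and leaves stopping to the Sponsor-Investigator's discretion. Items 7.5.2 and 8.5 require removal for any related Grade 4 non-hematologic toxicity. Two further removal criteria matter here: 7.5.3, "Development of any other unacceptable toxicities unless prophylactic measures can be taken for subsequent cycles", and 7.5.4, "Delay of a treatment cycle for more than 4 weeks due to adverse events".

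**The concern.** The second-occurrence action belongs to the weekly schedule. A site that follows Table 1 to the letter in Arm B reaches an instruction with nothing to act on. No other section supplies a BV action in its place: the package-insert reference in 7.1 is for nivolumab only, 8.5.1 deals with delay and removal but gives no BV dose level, and the contact for dosing questions in 7.1 is not a written rule.

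The toxicity is foreseeable. All patients have had BV before, and 5.2.7 admits those with Grade 1 neuropathy due to BV. At stake is consistent handling of a patient whose Grade 2 neuropathy recurs at the reduced dose: as written, that patient recovers and returns to the dose on which the event recurred.

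**Working it through.** **Which step works in which arm.** Inputs are the Schema, 7.2, 7.3 and Table 1. Planned BV intensity is dose × doses per cycle ÷ weeks per cycle.

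| Step | Arm B (Day 1 of 21) | Arm A (Days 1, 8, 15 of 28) |
|---|---|---|
| Start | 1.8 ÷ 3 = 0.6 mg/kg/week | 3 × 1.2 ÷ 4 = 0.9 mg/kg/week |
| First: reduce to 1.2 mg/kg | 1.2 ÷ 3 = 0.4 (cut of 33%) | 0.9 (no change; already 1.2 mg/kg) |
| Second: omit Day 8 | 0.4 (no change; no Day 8 dose) | 2 × 1.2 ÷ 4 = 0.6 (cut of 33%) |
| Third | removal | removal |

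The table mixes the arms: the first step has an effect only in Arm B, the second only in Arm A. Each arm gets one effective reduction before removal.

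**How many patients could reach the empty step.** The plan gives no Grade 2 rate, so the risks here are assumptions. Let p be the risk of a Grade 2 event after each dose before the first event, and rp the risk after it. Assume four doses and recovery in time to be re-dosed. The step matters only if a second event occurs with a dose still to come, so two events are needed among doses 1 to 3:

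P(reach) = rp²(3 − p − rp), which is 3p² − 2p³ when r = 1.

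At p = 10% and r = 1: 3(0.01) − 2(0.001) = 0.028, and 20 × 0.028 = 0.56 patients.

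| Expected patients of 20 | p = 5% | p = 10% | p = 20% |
|---|---|---|---|
| Risk falls with the dose cut (r = 2/3) | 0.10 | 0.38 | 1.4 |
| Constant risk (r = 1) | 0.15 | 0.56 | 2.1 |
| Risk doubles (r = 2) | 0.29 | 1.1 | 3.8 |
| Constant risk, split evenly between motor and sensory and counted per row | 0.07 | 0.29 | 1.1 |

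The last line uses q = p/2 in each row and 1 − (1 − 3q² + 2q³)². At p = 10%: 3(0.0025) − 2(0.000125) = 0.00725 per row, 1 − 0.99275² = 0.01445, and 20 × 0.01445 = 0.29. If half the patients stop for progression after cycle 2 (also an assumption), every entry halves. Failure to recover in time lowers them further, because it leads to removal under 7.5.4.

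**What third-occurrence removal can still do.** With four doses it can spare only dose 4, and only after events following doses 1, 2 and 3. Under constant risk, its share of the patients reached is p³ ÷ (3p² − 2p³) = p ÷ (3 − 2p): 1.7%, 3.6% and 7.7% at 5%, 10% and 20%.

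**Grade 4.** Table 1 allows discretion, while 7.5.2 and 8.5 require removal. The two can be read together with the removal rule governing, so this is a wording mismatch.

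**The case against.** The strongest reply is that little is left unprotected. Each Grade 2 event triggers a hold until Grade 1 or less or baseline, the dose stays at 1.2 mg/kg, a delay of more than 4 weeks means removal, unacceptable toxicity means removal, and treatment ends at four doses. Section 12 also makes continuation after cycle 2 depend on the absence of unacceptable toxicity. All of this stands. A reader might infer that the Day 8 step was the main limit on further BV, or that patients would be re-dosed with unresolved neuropathy. The documents support neither: nobody is re-dosed while a treatment-emergent neuropathy is above both Grade 1 and baseline.

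A reader might also infer from the 0% against 33% contrast at step two that Arm B is handled more loosely than Arm A was. That does not follow. Step one did nothing in Arm A, and an Arm B patient after step one is at 0.4 mg/kg/week, against 0.6 for an Arm A patient after step two.

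The upper reach figures also need caution. A constant 20% risk per dose implies that 1 − 0.8⁴ = 59% of patients have a Grade 2 event within four doses. The only neuropathy figure in the plan, in section 2.3, is Grade 3-4 sensory neuropathy in 8-10%, with up to 16 cycles in the Hodgkin's lymphoma study. That is not a Grade 2 rate, but nothing in the plan supports the top of the range.

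None of this makes the instruction workable. It is an operative safety rule that does nothing when followed exactly in the only open arm.

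**Conclusion.** The defect is confirmed, and it is minor. In Arm B a second Grade 2 neuropathy leads to a hold and then, after recovery, to the same 1.2 mg/kg every 3 weeks, with no further step before removal at a third occurrence.

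Probably fewer than one or two of 20 patients would reach this step. That is a judgement on assumed risks: under constant risk the expected number is below one at 5% or 10% per dose and about two at 20%; it approaches four only if a 20% risk doubles after the first event. A reader might go on to infer that the response rate or the 40% success threshold for Arm B is affected. Nothing in the documents shows that.

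**What to change.** In both rows of Table 1, give Arm B a second-occurrence step that can be carried out. The documents define no BV dose below 1.2 mg/kg, so the simplest text is *Second occurrence: remove from protocol treatment*, with the third-occurrence line deleted. Alternatively, the sponsor may name a lower BV dose or a longer interval and keep removal at the third occurrence; that choice needs a clinical rationale which the plan does not now contain.

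In the same amendment, split the last column: Grade 3 stays at the Sponsor-Investigator's discretion, and Grade 4 reads *remove from protocol treatment (see 7.5.2 and 8.5)*.

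The cost is a few words in each row, with no extra patients, visits or scans. CT is already required after cycle 2 and 3 to 5 weeks after the last cycle. The downside of removal is that an affected patient forgoes at most doses 3 and 4 of both drugs on protocol, so a late response could be missed. Compared with the present rule, under constant risk the expected loss is 20 × p²(4 − 3p) dosing days: 0.19, 0.74 or 2.7 of 80 planned (0.2%, 0.9% or 3.4%) at 5%, 10% or 20%. Section 7.2 allows other therapy after protocol treatment and nivolumab is commercial supply (3.1), so a physician could still give nivolumab alone off protocol.

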8.5 Modifications for Other Adverse Events

The patient will be removed from protocol treatment for any related Grade 4 non-hematologic toxicity or other dose-limiting toxicity as described.

- 8.5.1 Patients should receive appropriate medical management for adverse events. Treatments may be delayed for clinically significant Grade 2 or 3 adverse events and unrelated Grade 4 adverse events at the discretion of the treating physician. If treatment cycles are delayed for more than 4 weeks due to adverse events, the patient will be removed from protocol treatment.
- 8.5.2 Management of nivolumab-related adverse events should be per standard of care.

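### Table 1 (section 8.4) leaves stopping for related Grade 4 neuropathy to discretion, which contradicts the removal rule in 7.5.2; for Grade 3 it sets no conditions if treatment continues

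*Combined protocol and SAP*

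**What the plan says.** Section 8.4 governs neuropathy attributed to study treatment. A note above Table 1 says that its rules apply to every "dose of study drug and are relevant for treatment-emergent AEs only". The table has one column for Grade 1, one for Grade 2, and a single shared column for Grades 3 and 4. In both the motor and the sensory row, the shared column reads "Discontinue treatment at the discretion of the Sponsor-Investigator" and nothing more.

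The Grade 2 column is much more specific. It orders a hold until the event is Grade 1 or lower or back to baseline, a reduction to 1.2 mg/kg at the first occurrence, a further step at the second, and removal at the third.

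Three of the removal criteria listed in section 7.5 bear on this. The one that matters most is 7.5.2: "Development of any related Grade 4 non-hematologic toxicity or other dose limiting toxicity as defined under section 8.0". Item 7.5.3 is a catch-all for toxicity judged unacceptable, and it does not apply where prophylaxis could protect the patient in later cycles. Item 7.5.4 sets a time limit, and removes a patient once a cycle has been held up by toxicity for longer than 4 weeks.

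Section 8.5, headed "Modifications for Other Adverse Events", opens with a rule like that of 7.5.2: "The patient will be removed from protocol treatment for any related Grade 4 non-hematologic toxicity". Its item 8.5.1 adds that "Treatments may be delayed for clinically significant Grade 2 or 3 adverse events", and leaves that decision to the physician in charge of treatment.

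**The concern.** At Grade 4 the protocol gives two different answers to the same question. Section 14.1 defines Grade 4 as life-threatening or disabling. For every other related non-hematologic toxicity of that grade, removal is automatic. For neuropathy, the table written specifically for it makes stopping a matter of judgment.

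At Grade 3 the written rule thins out just as severity rises. Grade 2 carries a compulsory hold, a recovery level and a dose. Grade 3 carries an instruction to stop that may be waived, with nothing to govern a patient for whom it is waived.

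Neuropathy is a foreseeable event here. Section 2.3 names peripheral sensory neuropathy among the common Grade 3-4 events with brentuximab vedotin, and every patient has had the drug before. Exclusions 5.2.7 and 5.2.8 limit the risk, but they still admit Grade 1 neuropathy due to the drug and Grade 2 neuropathy from other causes.

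**Working it through.** The plan gives no figure to reproduce. The check is to set the texts side by side.

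**Grade 4**

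1. *Does 7.5.2 cover the event?* Table 1 is confined to treatment-related neuropathy, so the event is related. Neuropathy is non-hematologic. A Grade 4 event in Table 1 therefore meets every term of 7.5.2.
2. *Is 7.5.2 limited to infusion reactions, since it is numbered under 7.5?* No. The same list includes disease progression and completion of all four cycles, so it is a general list of removal criteria.
3. *Is neuropathy excepted?* Neither 7.5.2 nor section 8.4 says so.
4. *Do the two texts agree?* No. 7.5.2 makes the event a removal criterion without reference to judgment; Table 1 makes stopping discretionary.
5. *Does any text set an order of precedence?* None was found.
6. *Is section 8.5 needed for this conclusion?* No. It repeats the rule, but the word 'Other' in its heading may exclude neuropathy. The conflict rests on 7.5.2 alone.

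**Grade 3, if the Sponsor-Investigator does not stop treatment**

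| Text | Hold required? | Recovery level? | Dose stated? |
|---|---|---|---|
| Table 1, Grade 2 (first occurrence) | Yes | Grade 1 or lower, or baseline | 1.2 mg/kg |
| Table 1, Grade 3 | No | None | None |
| 7.5.3 | No; removal if judged unacceptable, with an exception for prophylaxis | None | None |
| 7.5.4 | No; limits the length of a delay | None | None |
| 8.5.1 | No; a delay is permitted, under the 'Other' heading | None | None |

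7.5.2 also removes patients for dose-limiting toxicity as section 8 defines it, but nothing in section 8 labels Grade 3 neuropathy as dose limiting. No text therefore supplies the missing conditions.

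**Extent.** The shared column appears in two rows, motor and sensory. With at most 4 cycles, the question can arise at no more than 4 - 1 = 3 re-dosing decisions per patient. The documents do not allow a patient count. The 8-10% in section 2.3 pools Grades 3 and 4 and draws on studies that include one of up to 16 cycles.

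**The case against.** The best defense at Grade 4 is that no text orders anyone to continue. Removing the patient satisfies both Table 1 and 7.5.2, the table's title calls its contents guidelines, and the decision belongs to the Sponsor-Investigator. Section 7.1 also names a contact for dose-modification questions. This is fair as far as it goes: a careful Sponsor-Investigator would probably remove the patient, and a reader should not infer that staff are under opposing orders. The mismatch remains, because Table 1 permits a choice that 7.5.2 does not. If the specific table overrides the general rule, neuropathy has a weaker stop rule than any other related Grade 4 non-hematologic event. If 7.5.2 overrides, the table is wrong as written, and the note above it calls its contents rules.

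At Grade 3 the defense is stronger. The listed action is to stop, and leaving the exception to the Sponsor-Investigator is a legitimate choice in a pilot of up to 20 patients per arm. The shared cell might even be what 7.5.2 means by dose-limiting toxicity, although no label says so.

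A reader might go further and infer that a Grade 3 event that has recovered to Grade 1 falls into the Grade 1 column, so that the table directs re-dosing at the full 1.8 mg/kg. The documents do not support that. The Grade 2 cell counts occurrences, so its actions attach to the event and not only to the grade on the next dosing day. Read the other way, a Grade 2 event that had recovered to Grade 1 would also escape its ordered reduction. What stands is narrower: the plan is silent on the conditions for continuing.

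**Conclusion.** The Grade 4 contradiction is established by the text and carries the point. It assumes only that treatment-related neuropathy is a related, non-hematologic toxicity, and that 7.5.2 means what it says.

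The Grade 3 gap is real but secondary. It matters only when the Sponsor-Investigator decides against the listed action.

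Its size is that of a defect in a safety rule, not a numerical effect. A figure for excess brentuximab vedotin exposure would need several assumptions at once: an early Grade 3 event, a waived stop, no reduction, and all remaining doses given in full. None is claimed. Arm B's planned 20 patients and its 40% success threshold (section 13.1) are unaffected. The correction should be made at the next amendment.

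**What to change.** Split the shared Grade 3 and Grade 4 column in both the motor and the sensory row.

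- **Grade 4:** *Discontinue protocol treatment (7.5.2).*
- **Grade 3:** *Discontinue treatment. If the Sponsor-Investigator elects to continue, withhold brentuximab vedotin until Grade 1 or lower or baseline, within the 4-week limit of 7.5.4, then resume at no more than 1.2 mg/kg.*

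The Grade 3 recovery level and dose are those the table already uses for a first Grade 2 event, so no new threshold is introduced. Whether a patient already reduced to 1.2 mg/kg should stop outright after a Grade 3 event is a further choice for the Sponsor-Investigator; the present table does not settle it.

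The cost is the wording of one table column. No patients, visits or procedures are added. The downside is slightly less case-by-case discretion: none at Grade 4, where 7.5.2 already allows none, and minimum conditions at Grade 3.
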